5.12. Subgroup Analyses

Population subgroups of interest will be analyzed for the variable of HbA1c.

The following are candidate subgroups that might be analyzed. This list is not necessarily all-inclusive:

- Sex
- Baseline age group (<65 years, \geq 65 years)
- Duration of diabetes at baseline (<median duration and \geq median duration)
- Baseline body mass index (<median and \geq median)
- Baseline HbA1c strata (<8.5%, \geq 8.5%)
- Baseline FSG (by quartile)
- Baseline insulin dose (<median and \geq median)
- OAM usage (metformin alone, acarbose alone, metformin and acarbose), if more than 20 patients in each subgroup stratum.

An analysis will be performed examining the interaction term of the treatment by subgroup at Week 28 using the MMRM model with treatment, OAM usage, visit, subgroup, subgroup-by-treatment interaction, treatment-by-visit interaction, subgroup-by-visit interaction, and subgroup-by-treatment-by-visit interaction as fixed effects, baseline HbA1c as a covariate and patient as a random effect. For the subgroup analysis of baseline HbA1c strata (<8.5%, \geq 8.5%), the model will include treatment, OAM usage, visit, subgroup, subgroup by treatment interaction, treatment-by-visit interaction, subgroup-by-visit interaction, and subgroup-by-treatment-by-visit interaction as fixed effects. Baseline HbA1c will not be included as a covariate. The interaction effect will be evaluated using a significance level of 0.10, unadjusted. If the subgroup is one of the stratification variables, then the subgroup will only be included once in the model.

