10.3.3. Efficacy Analyses

10.3.3.1. Primary Analyses

The primary outcome is the difference in HbA1c change from baseline between treatment groups based on the ITT population at the planned end of the treatment period of 28 weeks. The analysis model will be a MMRM for HbA1c change from baseline to 28 weeks (Visit 17) in the ITT population with treatment, OAM use, visit and treatment-by-visit as fixed effects, baseline HbA1c as a covariate, and patient as a random effect.

The analysis model, MMRM, will be repeated using the PP and Completers populations. If the conclusion differs from that of the ITT population, the data and analyses will be further investigated.

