10.3.7.2. Subgroup Analyses

Subgroup analyses of treatment interaction with important factors may be conducted for the primary endpoint of HbA1c. The model for the primary analysis will be an MMRM utilized by adding additional factors of subgroup, subgroup by treatment, subgroup by visit and treatment by subgroup by visit when accessing the treatment by subgroup interaction. If the subgroup is one of the stratification variables, then the subgroup will only be included once in the model.

The following are candidate subgroups that might be analyzed. This list is not necessarily all-inclusive:

- Sex
- Baseline age group (<65 years, \geq 65 years)
- Duration of diabetes at baseline (<median duration and \geq median duration)
- BMI at baseline (<median and \geq median))
- Baseline HbA1c (<8.5%, \geq 8.5%)
- Baseline fasting glucose (by quartile)
- OAM usage (metformin alone, acarbose alone, metformin and acarbose), if more than 25% of the total patients

10.3.8. *Interim Analyses*

No interim analyses are planned for this study. If an unplanned interim analysis is deemed necessary, the appropriate Lilly medical director, or designee, will be consulted to determine whether it is necessary to amend the protocol.

11. References

[ADA] American Diabetes Association. Glycemic targets: Standards of medical care in diabetes-2020. *Diabetes Care* 2020 Jan; 43(Supplement 1):S66-S76.

[ADA] American Diabetes Association. Pharmacologic Approaches to Glycemic Treatment: Standards of Medical Care in Diabetes-2019. *Diabetes Care* 2019 Jan; 42(Supplement 1): S90-S102.

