5.2. General Considerations

This plan describes all priori statistical analyses for efficacy and safety that will be performed.

Statistical analysis of this study will be the responsibility of Eli Lilly and Company (Lilly), although implementation of the statistical analysis may be delegated to a third party. Any change to the data analysis methods described in the protocol will require an amendment ONLY if it changes a principal feature of the protocol. Any other change to the data analysis methods described in the protocol, and the justification for making the change, will be described in this SAP and/or in the clinical study report (CSR). Additional exploratory analyses of the data will be conducted, as deemed appropriate.

All analyses will be implemented using Version 9.4 SAS or higher.

Unless otherwise specified, listings will include all randomized patients. Both efficacy and safety analyses will be conducted using the intent-to-treat (ITT) population. Unless otherwise specified, efficacy data from patients who started rescue therapy or premature treatment discontinuation (whichever occurs first) will be censored from the point of initiating rescue treatments or early discontinuation onwards. Safety analysis will not censor this part of data. Selected analyses will also be conducted using the per-protocol (PP) and Completers populations. The PP and Completers populations are subsets of the ITT population.

Unless otherwise noted, all tests of treatment effects will be conducted at a 2-sided alpha level of 0.05, and confidence intervals (CIs) will be calculated at 95%, 2-sided. All tests of interactions between treatment groups and other factors will be conducted at a 2-sided alpha level of 0.10.

The baseline data will be collected at Visit 3. For all variables, including HbA1c, if baseline data are missing, the last non-missing measurement taken prior to this visit will be used for the baseline measurement.

Patients will be randomized in a 1:1 ratio to (1) dulaglutide 1.5 mg QW add-on to insulin glargine or (2) placebo QW add-on to insulin glargine, with metformin and/or acarbose. Patients will also be stratified by HbA1c at Visit 1 (screening) (<8.5% vs. \geq 8.5%) and OAM usage (metformin alone, acarbose alone, metformin and acarbose) at Visit 3 (randomization) to achieve

between-group comparability and to mitigate against confounding the effects of the treatments with severity of disease or treatment with metformin and/or acarbose.

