The primary analysis model will be mixed-model for repeated measures (MMRM) analysis using restricted maximum likelihood (REML) with treatment, OAM usage (metformin alone, acarbose alone, metformin and acarbose), visit, and treatment-by-visit interaction as fixed effects, baseline HbA1c as a covariate, and patient as a random effect. An unstructured covariance structure will be used to model the within-patient variability and implicitly adjust for missing data. There will be no imputation of missing data for patients who have no postbaseline data.

If this analysis fails to converge, the following covariance structures will be tested in order:

- Toeplitz with heterogeneity
- Autoregressive with heterogeneity, by visit
- Compound symmetry with heterogeneous variances, by visit
- Toeplitz
- Autoregressive
- Compound symmetry without heterogeneous variances, by visit

The first covariance structure that converges will be used. The Kenward-Roger approximation will be used to estimate denominator degrees of freedom. Significance tests will be based on least-squares (LS) means using Type III hypotheses.

The percentage of patients achieving the target HbA1c of <7.0% will be analyzed using a longitudinal logistic regression with repeated measurements.

For continuous measures, summary statistics will include sample size (n), mean, SD, median, minimum (min), and maximum (max) for both the actual and the change from baseline measurements. Least-squares mean (LS Mean) and standard errors (SEs) derived from the model will also be displayed for the change from baseline measurements. Treatment comparisons will be displayed showing the treatment difference LS Mean and the 95% CIs for the treatment differences along with the p-values for the treatment comparisons.

For categorical measures, summary statistics will include sample size, frequency, and percentages. Fisher's exact test will be used.

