5.6. Primary Efficacy Analysis

The primary efficacy measurement in this study is change in HbA1c from baseline to Week 28, as determined by the central laboratory.

The primary analysis model will be MMRM for HbA1c change from baseline to Week 28 (Visit 17). The model will include treatment, OAM use, visit, treatment-by-visit interaction as fixed effects, and baseline HbA1c as a covariate and patient as a random effect. LS Mean, 95% CI and the p-value will be presented for the treatment difference (dulaglutide 1.5 mg minus placebo).

Primary analysis will be done using ITT population.

The MMRM analysis model for the primary endpoint will be repeated using the PP and Completer populations to check the sensitivity of the primary analysis.

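### SAP 5.12 drops continuous baseline HbA1c from the HbA1c-strata subgroup model only, a small and avoidable loss of precision

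*SAP*

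**What the plan says.** Protocol 10.3.7.2 describes the subgroup model as an extension of the primary one: "The model for the primary analysis will be an MMRM utilized by adding additional factors of subgroup, subgroup by treatment", followed by the interactions with visit. It names terms to add and none to take away.

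The primary model contains the continuous covariate in both documents. Protocol 10.3.3.1 has "baseline HbA1c as a covariate, and patient as a random effect"; SAP 5.6 has "treatment-by-visit interaction as fixed effects, and baseline HbA1c as a covariate and patient as a random effect".

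SAP 5.12 follows this for the other subgroups and then makes one exception. The general model ends, and the exception begins, at "as fixed effects, baseline HbA1c as a covariate and patient as a random effect. For the subgroup analysis of baseline HbA1c strata". For those strata the SAP lists the same fixed effects and adds that "Baseline HbA1c will not be included as a covariate". No reason is given there.

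Both documents also carry a rule on duplicated terms: "If the subgroup is one of the stratification variables, then the subgroup will only be included once in the model".

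**The concern.** The SAP departs from the protocol's build rule for one subgroup, without explanation. In that model a two-level indicator is the only adjustment for baseline HbA1c. Variation in baseline within each stratum, which probably predicts HbA1c change, goes into the residual. Three things follow:

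- the interaction test and the within-stratum treatment differences are less precise than they could be with data already collected;
- chance imbalance in baseline HbA1c within a stratum is not adjusted for;
- this subgroup is adjusted differently from the primary analysis and from every other subgroup.

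Randomisation still protects the treatment comparison within strata, so bias is not at stake.

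**Working it through.** **1. Does the only-once rule require the removal?** Three facts, read together, say no.

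- The primary model has no HbA1c stratum term (Protocol 10.3.3.1, SAP 5.6), so adding the subgroup factor duplicates nothing.
- The randomisation factor is the screening category: SAP 5.2 has "Patients will also be stratified by HbA1c at Visit 1 (screening"). The subgroup is based on baseline HbA1c, and both documents set baseline at Visit 3.
- The rule limits how often the subgroup factor enters. It does not mention a continuous covariate.

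**2. The plan's own figure.** The documents state no figure for this model, but the sample size supplies the SD and the number of completers used below. With difference 0.5, SD 1.2, two-sided alpha 0.05 and 90% power:

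n per group = 2 × (1.960 + 1.282)² × 1.2² / 0.5² ≈ 121.1, rounded up to 122.

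The stated 123 per group has power 0.904 (normal) or 0.902 (noncentral t). Then 246/(1 - 0.15) = 289.4, or 290 randomised, and 290/(1 - 0.40) = 483 screened. All stated figures reproduce, and none depends on the covariate at issue.

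**3. Precision of the interaction.** Inputs:

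- From the documents: SD of change 1.2 (variance 1.44), 246 completers, 1:1 allocation, cut at 8.5%, interaction test at 0.10.
- Assumed: baseline HbA1c normal with mean 8.2 to 8.8 and SD 0.8 to 1.2, truncated to 7–11% (the eligibility range at screening, applied here to baseline). Slope of change on baseline, b, -0.4 to -0.8, common to both strata.

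Let Vx be the variance of baseline, Vw its pooled variance within strata, and p the proportion at or above 8.5%.

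- Residual variance with the covariate: 1.44 - b²Vx.
- Residual variance with the stratum only: 1.44 - b²Vx + b²Vw.
- Interaction SE: √[4 × residual variance / (246 × p × (1 - p))].
- Power for interaction D: Φ(D/SE - 1.645) + Φ(-D/SE - 1.645).

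Worked case (mean 8.5, SD 1.0, b = -0.6): Vx = 0.729, Vw = 0.245, p = 0.533.

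- With: 1.44 - 0.36 × 0.729 = 1.178, so SE = √[4 × 1.178/(246 × 0.249)] = 0.277.
- Without: 1.178 + 0.36 × 0.245 = 1.266, so SE = 0.288.
- SE ratio: √(1.266/1.178) = 1.037.
- Power for D = 0.5: 0.56 with, 0.54 without.

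Across the 27 combinations (three means, three SDs, slopes -0.4, -0.6 and -0.8):

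| Quantity | Smallest effect | Worked case | Largest effect |
|---|---|---|---|
| Mean / SD / slope | 8.2 / 0.8 / -0.4 | 8.5 / 1.0 / -0.6 | 8.8 / 1.2 / -0.8 |
| Residual variance ratio | 1.020 | 1.075 | 1.237 |
| Interaction SE, with → without | 0.307 → 0.310 | 0.277 → 0.288 | 0.245 → 0.272 |
| SE ratio | 1.010 | 1.037 | 1.112 |
| Power, D = 0.5, with → without | 0.495 → 0.488 | 0.563 → 0.538 | 0.655 → 0.576 |
| Power, D = 0.25, with → without | 0.210 → 0.208 | 0.234 → 0.225 | 0.270 → 0.239 |

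This is a single-visit approximation at Week 28, not the full repeated-measures model.

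**4. Can both terms be fitted?** Yes. The correlation of the 8.5% indicator with continuous baseline is about 0.78 to 0.83 over the same range.

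**5. Effect on LS means of keeping the covariate.** SAP 5.2 says "Least-squares mean (LS Mean) and standard errors (SEs) derived from the model will also be displayed for the change from baseline measurements". In the worked distribution the overall mean baseline is 8.62% and the stratum means are 7.88% and 9.27%. The overall mean therefore lies outside the lower stratum. At b = -0.6, evaluating LS means at 8.62% rather than at the stratum mean would shift them by -0.6 × (8.62 - 7.88) = -0.44 points in the lower stratum and -0.6 × (8.62 - 9.27) = +0.39 in the upper. Both arms of a stratum shift equally, so treatment differences and the interaction do not move.

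**The case against.** The best defence is that this is a prespecified and coherent choice. The sponsor uses the baseline HbA1c stratum as the modelling form of the HbA1c stratification factor; the protocol amendment log records the move from screening to baseline stratum in other models. On that view, entering HbA1c once, as the stratum, is what the only-once rule intends. SAP 5.2 also lets the SAP change non-principal methods, with the justification given in the SAP or the clinical study report, and the revision history lists only key changes, so its silence proves nothing. Omitting the covariate also avoids the LS-mean difficulty shown above. Finally, the stratum already captures about 66% of baseline variance in the worked case (1 - 0.245/0.729).

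Much of this stands. The choice is permissible and unbiased, and the loss is small. What does not stand is that the rule requires it: there is no stratum term in the primary model to duplicate, and one line of text settles the LS-mean question.

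A reader might infer a larger loss by assuming a baseline-to-change correlation of -0.7. With baseline SD 0.854 and SD of change 1.2, that implies a slope of -0.7 × 1.2/0.854 = -0.98, and Week 28 HbA1c almost uncorrelated with baseline (about 0.02). The documents give no support for so extreme a value.

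**Conclusion.** The point holds as a minor one. SAP 5.12 removes a covariate that the protocol's build rule retains, for one subgroup and without a stated reason. On the assumed inputs the interaction SE is about 1% to 11% larger, and power for a 0.5-point interaction is about 1 to 8 percentage points lower. That interaction is as large as the whole treatment effect for which the trial is sized; at 0.25 points the loss is at most about 3 percentage points, and power is low either way. These ranges rest on the assumed baseline distribution and slopes.

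A reader might infer that the subgroup result is biased or that the trial's main conclusions are weakened. The documents do not support either. The analysis is only a candidate one, tested without multiplicity adjustment, and the primary and Type I error-controlled analyses do not use this model.

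A reader might also see the missing baseline hypoglycaemia rate in SAP 5.11.2 as a fault of the same kind. It is not: the SAP revision history discloses that a covariate was removed from that model, SAP 5.2 allows the reason to appear in the study report, and the protocol does not define that rate.

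**What to change.** In SAP 5.12:

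- delete the sentence "Baseline HbA1c will not be included as a covariate" and keep continuous baseline HbA1c in the model alongside the stratum and its interactions;
- add one line saying that within-stratum LS means are evaluated at the stratum-specific mean baseline HbA1c, and that treatment differences and the interaction test are read as usual.

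The cost is one model degree of freedom and one line of text. No new data and no protocol amendment are needed, because the change returns the SAP to the protocol's rule. It should be settled before unblinding. If the sponsor prefers the omission, SAP 5.12 should give the reason. No change is needed in SAP 5.6 or 5.7.

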5.13. Patient-Reported Outcome Analyses

The exploratory patient-reported outcome (PRO) analyses will be analyzed using the ANCOVA model with fixed effects treatment, OAM usage, baseline HbA1c strata (<8.5%, \geq 8.5%) and baseline score as a covariate, using on-treatment without rescue data. LOCF will be used to impute missing postbaseline values, and treatment contrasts will be computed.

Questionnaire-specific analyses are summarized as follows:

- EQ-5D-5L: Summary statistics, including number of patients and proportion of categorical outcomes (5 levels) for the 5 dimensions (mobility, self-care, usual activity, pain/discomfort, and anxiety/depression) of EuroQol 5-dimension 5-level (EQ-5D-5L) questionnaire will be provided by treatment, at baseline, Week 12 and Week 28. Summary statistics of actual value and the changes from baseline to Week 12 LOCF endpoint and Week 28 LOCF endpoint in the EQ-5D-5L UK and Chinese population-based health state index score and EuroQol visual analog scale (EQ-VAS) score will be

summarized. EQ-5D-5L Chinese Population-based index score (Luo et al. 2017) can be derived to produce a patient-level index score between 0 and 1: <https://ars.els-cdn.com/content/image/1-s2.0-S1098301516341250-mmc1.xls>. The changes from baseline will be analyzed using the ANCOVA model for UK and China Index score and VAS score.

- IW-SP: Total score will be calculated, and mean, SD, min, and max scores for each domain will be provided by visit and by treatment. Mean, SD, median, min, and max scores will be provided for changes from baseline to Week 12 (Visit 12) and Week 28 (Visit 17). An ANCOVA model for the changes from baseline to Weeks 12 and 28 will be conducted. Significance of changes within each treatment arm and significance of difference between treatment groups will be reported.

The modules within the MDDAB (Modules 1, 2, 3a, 3b, and 4) will be evaluated as exploratory objectives in this study. The planned reports for each module by visit are as follows:

- Module 1, SUP ease of use: Each item in the module will be summarized using descriptive statistics (number of patients, mean, SD, median, first quartile, third quartile, min, and max) and frequencies and percentages of responses for each of the 5 categorical response options. Frequencies and percentages of patients who responded “Easy” or “Very Easy” will be summarized for each item.
- Module 2, SUP device features: Each item in the module will be summarized individually using descriptive statistics (number of patients, mean, SD, median, first quartile, third quartile, min, and max) and frequency counts and percentages of responses for each of the 5 response options. Additionally, frequency counts and percentages of patients who responded “Like” or “Extremely Like” will be summarized for each item.
- Modules 3a and 3b, SUP experience modules (3a: Visit 8 [Week 6] assessment; 3b: Week 28 and ET assessment): each item will be summarized individually using descriptive statistics (number of patients, mean, SD, median, first quartile, third quartile, min, and max) and frequency counts and percentages of responses for each of the response options. Additionally, frequency counts and percentages of patients who responded “Strongly Agree” or “Agree” (Items 1-3); “Confident,” “Very Confident,” or “Extremely Confident” (Items 4-6); “Mostly Willing” or “Definitely Willing” (Items 7-8) will be summarized.
- Module 4, Glargine delivery device experience module, will be summarized in the same way as module 3b (SUP experience module for end of study and ET). No formal statistical testing will be conducted to compare experience with the SUP at end of study (Module 3b) and experience with the glargine delivery device at end of study (Module 4); the study is not designed for comparative device evaluation, as patients will have uneven exposure to devices, both in terms of duration of use and frequency of administration.

6. Unblinding Plan

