The final office visit, Visit 17, will take place at Week 28 (± 7 days). Study procedures at this visit are shown in the Schedule of Activities (Section 2). The EQ-5D-5L, IW-SP, and MDDAB modules 1, 2, 3b, and 4 questionnaires will be completed before any other study procedures if the patient is not adversely affected by the fasting condition or completed after the patient has sufficiently recovered from the preceding visit procedures. A final physical examination will be performed, including weight and vital signs (sitting blood pressure [BP] and pulse rate [PR]) measurements and electrocardiogram (ECG) testing using the existing equipment at the site. Study drug will be discontinued and an appropriate diabetes treatment regimen will be prescribed per the investigator's judgment. A patient summary eCRF will be completed.

Study procedures will be performed per the Schedule of Activities (Section 2).

Study Period III (Safety Follow-Up Period):

Safety Follow-Up (801) Visit

All patients who complete the treatment period are required to complete Visit 801, a safety follow-up visit approximately 4 weeks after last visit. Patients discontinuing the study early and performing an early termination (ET) visit will also be asked to perform the safety follow-up visit, so that the safety follow-up visit will be their final visit. During the safety follow-up period, patients will not receive study drug. Patients may be treated with another glucose-lowering intervention decided upon by the investigator (see Section 7.7.1). Initiation of new antihyperglycemic therapy for the safety follow-up period will not be classified as "rescue therapy". Patients are required to return any remaining study diaries to the study site at the end of this period.

Early Termination Visit (If Necessary)

Every attempt will be made to keep patients in the trial irrespective of their adherence to treatment with study drug. At any time after Visit 3 (randomization), a patient who is to discontinue from the study before Visit 17 will have an early termination (ET) visit conducted. At this visit, procedures will occur as shown in the Schedule of Activities (Section 2). Patients

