- If an investigator, site personnel performing assessments, or patient is unblinded;
- If the investigator or sponsor decides that the patient should be withdrawn from study drug; if the investigator decides to permanently discontinue study treatment because of an SAE or a clinically significant laboratory value, Lilly or its designee should be alerted immediately.
- if the patient or the patient's designee, for example, legal guardian, requests that the patient be withdrawn from study drug

Patients who stop the study drug permanently will receive another glucose-lowering intervention (Section 7.7.1) and will continue participating in the trial according to the protocol to collect all planned efficacy and safety measurements.

Patients discontinuing from the investigational product prematurely for any reason should complete AE and other follow-up procedures per Section 2 Schedule of Activities, Section 9.2 Adverse Event, and Section 9.4 Safety of this protocol.

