The IW-SP questionnaire contains 3 items that assess how often patients body weight affects how happy they are with their appearance and how often they feel self-conscious when out in public (Hayes and DeLozier 2015). Items are scored on a 5-point numeric rating scale, where 5 = never and 1 = always. Overall score is calculated by summing the scores of the 3 items and dividing by the number of items (3). Overall score ranges from 1 to 5. Transformed overall score is obtained by linearly transforming the raw overall score to a 0 to 100 scale. Higher overall score and higher transformed score are indicative of better self-perception.

The IW-SP will be completed by the patients at Visits 3 (Week 0), 12 (Week 12), 17 (Week 28), and ET per the Schedule of Activities (Section 2).

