5.1. Determination of Sample Size

A total of approximately 290 patients (145 per group) will be randomized to have approximately 246 completers (123 per group) to show dulaglutide add-on titrated insulin glargine is superior to placebo add-on titrated insulin glargine with 90% power assuming a treatment difference of 0.5% in HbA1c reduction, standard deviation (SD)=1.2%, and dropout rate of 15%, and 2-sided alpha of 0.05. The screen failure rate is estimated as 40%. Approximately 483 patients will be screened.

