5.8.2. Analysis of 7-point SMBG profile

The 7-point SMBG profiles consist of pre-meal and 2-hour postprandial SMBG measurements for the morning, midday, and evening meals, and one measurement at bedtime. Patients will be asked to perform two 7-point SMBG profiles over a 24-hour period on 2 nonconsecutive days, in the 2-week period prior to prespecified office visits (Visits 3 [Week 0], 12 [Week 12], 17 [Week 28], and early termination [ET]). In general, the mean of the two daily values will be used for reporting purpose. If 7-point SMBG is not performed, then data from the most recent nonconsecutive 4-point SMBG (3 before each meal and one at bedtime) profiles can be used. If more than 2 SMBG profiles are available, the 2 most recent profiles on nonconsecutive days should be used.

The following variables for 7-point SMBG profile will be analyzed using MMRM model:

1. Pre morning meal BG (mg/dL)
2. 2-hour postprandial measurement for morning meal BG (mg/dL)
3. Pre midday meal BG (mg/dL)
4. 2-hour postprandial measurement for midday meal BG (mg/dL)
5. Pre evening meal BG (mg/dL)
6. 2-hour postprandial measurement for evening meals BG (mg/dL)
7. Bedtime BG (mg/dL)
8. Mean of all pre-meal BG (mg/dL)
9. Mean of all postprandial BG (mg/dL)
10. Mean of all meals 2-hour excursion (mg/dL)
11. Mean of all 7-point BG (mg/dL)

For before and 2 hours after meal BG and bedtime BG (Reports 1-7), the mean BG value at each visit is calculated as the average of 2 daily BG values. The change from baseline is calculated as the mean BG value at Week 12 and Week 28 minus the mean BG value at the baseline.

For mean of all pre-meal BG (Report 8), the pre-meal daily mean is calculated as the average BG values collected for before morning, midday and evening meals on a particular day. The mean of all pre-meal BG at each visit is calculated as the average of 2 pre-meal daily means. The change from baseline is calculated as the mean of all pre-meal BG at Week 12 and Week 28 minus the mean of all pre-meal BG at baseline.

For mean of all postprandial BG (Report 9), the post-meal daily mean is calculated as the average of 2-hour postprandial BG values of morning, midday and evening meals on a particular day. The mean of all postprandial meals BG at each visit is calculated as the average of 2 post-

meal daily means. The change from baseline is calculated as the mean of all postprandial BG at Week 12 and Week 28 minus the mean of all postprandial BG at baseline.

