For mean of all meals 2-hour excursion at each visit (Report 10), the daily mean for all meals is calculated as the average of glucose excursion for morning, midday and evening meals on a particular day. The mean of all meals 2-hour excursion at each visit is calculated as the average of 2 daily means. The change from baseline is calculated as the mean of all meals 2-hour excursion at Week 12 and Week 28 minus the mean of all meals 2-hour excursion at baseline.

For mean of all 7-point BG (Report 11), the daily mean is calculated as the average of 7 BG values collected on a particular day. The mean of all 7-point BG at each visit is calculated as the average of 2 daily means. The change from baseline is calculated as the mean of all 7-point BG at Week 12 and Week 28 minus the mean of all 7-point BG at baseline.

Actual and change from baseline of 7-point SMBG will be summarized using ITT population, and analyzed using MMRM with treatment, OAM usage, visit, baseline HbA1c strata (<8.5%, and $\geq 8.5\%$) and treatment-by-visit interaction as fixed effects, baseline 7-point SMBG as covariate and patient as a random effect. An unstructured covariance structure will be used to model the within-patient variability and implicitly adjusts for missing data. If this analysis fails to converge, then other covariance structures will be tested in the order mentioned in Section 5.2.

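### The exploratory EQ-5D-5L and IW-SP scores are analysed by ANCOVA with LOCF, although the MMRM in SAP 5.8.2 fits the same visits and avoids LOCF bias if data are missing at random

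*SAP*

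**What the plan says.** SAP 5.13 specifies an ANCOVA with treatment, OAM usage, baseline HbA1c stratum and baseline score, restricted to on-treatment data without rescue. Its missing-data rule is "LOCF will be used to impute missing postbaseline values, and treatment contrasts will be computed". For EQ-5D-5L it reports "changes from baseline to Week 12 LOCF endpoint and Week 28 LOCF endpoint". IW-SP changes to Weeks 12 and 28 go through the same type of model, with significance reported within and between arms.

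The questionnaires are collected at few visits. Protocol 9.9.2 says: "The IW-SP will be completed by the patients at Visits 3 (Week 0), 12 (Week 12), 17 (Week 28), and ET". The Schedule of Activities gives EQ-5D-5L the same visits. SAP 5.8.2 collects the 7-point SMBG profile at those visits too, but analyses it by MMRM with treatment, OAM usage, HbA1c stratum, visit, treatment-by-visit and baseline value: "An unstructured covariance structure will be used to model the within-patient variability and implicitly adjusts for missing data".

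Two other places bear on this. Protocol Appendix 7 records that ANCOVA with LOCF was removed for the primary and key secondary continuous measures because it could be biased; that change did not extend to the patient-reported outcomes. Protocol 10.3.7.1 refers the reader to an ANCOVA in Section 10.3.1, but the current 10.3.1 contains only an MMRM for continuous measures.

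**The concern.** Carry-forward is built into this design. A patient who stops study drug "will continue participating in the trial according to the protocol to collect all planned efficacy and safety measurements", and a rescued patient also stays in the trial. Scores after either event are excluded, so the last eligible score is normally Week 12. For someone leaving the study, "a patient who is to discontinue from the study before Visit 17 will have an early termination (ET) visit conducted", so an early-termination score may be carried instead, if it counts as on-treatment. The SAP does not say whether it does.

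Week 12 closes intensive insulin titration and Week 28 closes maintenance, so scores at the two visits need not be interchangeable. If they differ, and the arms carry forward at different rates or for score-related reasons, the Week 28 contrast can be biased in either direction.

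The Week 12 LOCF endpoint is also undefined as written. No questionnaire is scheduled between baseline and Week 12, so only an early-termination or baseline score could be carried to it, and the SAP has no rule for either.

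What is at stake is the reading of exploratory quality-of-life results. The primary, key secondary and safety conclusions are untouched.

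**Working it through.** **Inputs from the documents.** There are 145 patients per arm and a 15% dropout rate (SAP 5.1; 123/0.85 = 144.7, so 145). The documents give no figure for the patient-reported outcomes, and no rate for patients rescued or off drug who stay in the trial. Carry-forward of 5 to 20% per arm is therefore shown.

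**Assumed inputs** (0-100 scale, as for EQ-VAS or transformed IW-SP). Mean change at Weeks 12 and 28 is 4 and 8 on dulaglutide, and 2 and 4 on placebo. The true difference is thus 2 at Week 12 and 4 at Week 28. SD is 15 and the correlation between visits is 0.6.

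**Closed form, stopping unrelated to score.** Let the carried score lie a fraction f of the way from Week 12 to Week 28, and let m_d and m_p be the proportions carried on dulaglutide and placebo. Then

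LOCF difference = 4 − (1 − f)(4·m_d − 2·m_p).

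| m_d / m_p | Week 12 carried (f = 0) | Midway score carried (f = 0.5) |
|---|---|---|
| 15/15% | 4 − (0.60 − 0.30) = 3.70 | 3.85 |
| 20/10% | 4 − (0.80 − 0.20) = 3.40 | 3.70 |
| 10/20% | 4 − (0.40 − 0.40) = 4.00 | 4.00 |
| 5/20% | 4 − (0.20 − 0.40) = 4.20 | 4.10 |

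**Simulation** (3000 runs, Monte Carlo error about 0.03). The MMRM has a common baseline slope, treatment-by-visit and unstructured covariance. OAM usage and HbA1c stratum are not simulated. Every patient has a Week 12 score, and the MMRM does not use early-termination scores. Score-driven stopping has probability Φ(√2·Φ⁻¹(m) − z), with z the standardised Week 12 or Week 28 score. Entries are LOCF with Week 12 carried / LOCF with a midway score carried / MMRM; the truth is 4.

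| Stopping depends on | 15/15% | 20/10% | 5/20% |
|---|---|---|---|
| Nothing (random) | 3.68 / 3.83 / 3.97 | 3.37 / 3.67 / 3.99 | 4.21 / 4.12 / 4.02 |
| Week 12 score (missing at random) | 3.67 / 3.82 / 3.98 | 2.98 / 3.49 / 4.00 | 5.00 / 4.52 / 4.05 |
| Unseen Week 28 score (not at random) | 3.70 / 3.85 / 4.01 | 3.82 / 3.90 / 4.92 | 3.42 / 3.70 / 2.52 |

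Standard errors are 1.42 to 1.51 for MMRM and 1.37 to 1.50 for LOCF. The equal-rate bias of 0.15 to 0.30 is thus about 0.1 to 0.2 standard errors. The unequal, Week 12-driven bias (0.51 to 1.02 at 20/10%; 0.52 to 1.00 at 5/20%) is about 0.4 to 0.7.

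**Null case, in SD units.** With no treatment effect, a common change of 0.5 SD from Week 12 to Week 28 and about 20% versus 10% dropout, LOCF gives −0.05 to −0.07 SD with type I error 0.065 to 0.084. At an extreme split of about 25% versus 5% it gives −0.10 to −0.13 SD and 0.134 to 0.177. The MMRM holds 0.046 to 0.054.

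**The case against.** SAP 5.13 is a complete specification, and exploratory endpoints do not have to follow the primary method. LOCF also remains for laboratory analytes, so keeping it here is not a contradiction. That is right: this is a choice of analysis, not an error.

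At the only rate the documents give, 15%, and with equal stopping, the bias is trivial. With random stopping LOCF even has the lower root mean squared error, about 1.4 against 1.5. If the effect is already complete at Week 12 with no later drift, both methods are unbiased and LOCF rejects slightly more often (0.73 against 0.67 to 0.68 for an effect of 0.30 SD). This stands, and no precision gain is claimed for MMRM.

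The larger biases assume strong selection. At m = 20%, the formula has 52% of the lowest score quartile stopping against 1.2% of the highest, and rescue is triggered by glucose, not by a questionnaire. This reduces the size but not the direction. At 20/10% and 5/20% with Week 12 carried, LOCF gives 3.40 and 4.20 with no selection (closed form), 3.14 and 4.62 under a much weaker dependence, and 2.98 and 5.00 under the strong one. MMRM stays within 3.96 to 4.05 throughout.

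The most serious objection is that missing at random cannot be tested here, and when it fails MMRM can do worse: 4.92 and 2.52 in the unequal cases, against LOCF at 3.82 to 3.90 and 3.42 to 3.70. This also stands, and is why LOCF should be kept alongside. Finally, an MMRM without a rule for early-termination scores could lose patients whose only postbaseline score is from that visit.

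**Conclusion.** The concern holds as a minor point. ANCOVA with LOCF lets earlier scores stand in for Week 28, while a model that avoids this under missing at random is already specified in the same SAP for the same visits, with the same OAM and HbA1c-stratum terms. On the assumed scores, the bias is 0.15 to 0.30 points with equal carry-forward and up to about 1 point with unequal, strongly score-driven stopping. It is zero if scores are flat after Week 12 and stopping is unrelated to score. These sizes rest on assumed means, SD, correlation and stopping rates; the normal-score model represents EQ-VAS or transformed IW-SP rather than the EQ-5D-5L index. The preference for MMRM rests on missing at random.

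**What to change.** In SAP 5.13, make the SAP 5.8.2 MMRM the main analysis for the EQ-5D-5L index scores, EQ-VAS and IW-SP. Use treatment, OAM usage, HbA1c stratum, visit, treatment-by-visit and baseline score, with unstructured covariance and contrasts at Weeks 12 and 28. State the missing-at-random assumption and keep ANCOVA with LOCF as a sensitivity analysis.

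Alongside this:
- say which visit an early-termination score is assigned to and whether it counts as on-treatment;
- say whether a baseline score may be carried forward;
- correct the ANCOVA reference in Protocol 10.3.7.1.

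The cost is SAP wording, one protocol cross-reference and minor reprogramming that reuses the SMBG model. No new data are needed. Patients with no eligible postbaseline score still contribute nothing, and without the assignment rule those with only an early-termination score could be lost from the MMRM.
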